- 24-week change from baseline in physical function, measured with the PROMIS-PF Short Form 6b.
- 24-week change from baseline in depression score, measured with the PROMIS 4-item depression scale from the PROMIS 29 profile.
- 24-week change from baseline in anxiety score, measured with the PROMIS Emotional Distress-Anxiety scale (PROMIS-EDA 4a).
- 24-week change from baseline in sleep disturbance, measured with the PROMIS short form 6a.
- 24-week change from baseline in sleep duration, measured with the BACPAC sleep duration question.

Endpoints:

Study Population:

The study will enroll adult participants who report having low-back pain for at least 3 months and on at least half the days in the past 6 months. Participants must be at least 18 years of age and meet other inclusion/exclusion criteria as described in Section 8.

Sample Size:

The study will enroll approximately 820 participants in order to obtain approximately 630 completers (i.e., 10% post-Run-in ineligibility and an additional 15% dropout rate over the course of the trial assumed). Assuming dropout occurs uniformly across study interventions, the sample size of 630 will result in having approximately 80% probability of estimating a DTR within 90% of the optimal DTR based on the study's primary endpoint. Based on previous studies, it is estimated that approximately 200 participants will consent to undergo comprehensive phenotyping (i.e., phenotyping assessments beyond what is required for all participants). More details, including assumptions regarding intervention effect sizes can be found in Section 13.

Interim Analysis:

Generally, this trial will inform a precision medicine approach to the treatment of chronic low-back pain. In order to maintain sufficient power for the precision medicine analyses, interim analyses for futility or efficacy are not planned.

Final Analysis:

Q-learning^{5,6} will be used to estimate a two-stage dynamic treatment regime that assigns a sequence of cLBP treatments based on phenotypic markers and the patient's response to treatment in order to maximize the expected reduction in PEG between the beginning and the end of the study. Q-learning reduces the reinforcement learning problem of optimizing a two-stage dynamic treatment regime to a standard regression problem, after which standard regression algorithms can be applied.

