Participants may need to discontinue treatments prior to the end of the 12-week treatment period (e.g., following an adverse reaction to duloxetine; see Section 10.2.1 for list of reasons). Participants needing to discontinue first period treatment will be switched to a randomly selected second treatment at Visit 1. Participants needing to discontinue second period treatment will remain in the study and undergo all future assessments for which they are eligible.

The study will enroll approximately 820 participants in order to randomize approximately 740 individuals and to have approximately 630 completers (i.e., 15% dropout rate after randomization assumed). Assuming dropout occurs uniformly across study interventions, the sample size of 740 randomized will result in having approximately 80% probability of estimating a DTR within 90% of the optimal DTR based on the study's primary endpoint. See Section 13.2 for additional details on sample size needs for precision medicine objectives, including assumptions regarding intervention effect sizes.

The interventions under evaluation are evidence-based, with established efficacy and are standard of care. Therefore, we do not expect they will pose safety risks such that these interventions need to be stopped before the end of the study. Safety data and adverse events will be monitored. These data will be reported to and reviewed by a Data Safety and Monitoring Board. Generally, this trial will inform a precision medicine approach to the treatment of chronic low-back pain and therefore we are not planning interim analyses for futility or efficacy in order to maintain sufficient power for the precision medicine analyses. Blinding is not feasible for study participants or staff involved in the delivery of interventions. Investigators involved in the analysis of study data will be blinded to treatment assignment.

The study timeline involves approximately 9 months of participant enrollment across 12 sites for a total of 820 enrolled. Sites will enroll ~7 participants per month. We anticipate that ~90% of participants who consent at the Enrollment Visit will be randomized at the end of the 2-week run-in at Visit 0 and that 85% of randomized participants will complete all study activities. The total study duration for all participants is 38 weeks. To minimize participant burden, where possible, data will be collected remotely.

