13.2. SAMPLE SIZE DETERMINATION

Simulation Methodology Overview

Simulation studies were used to determine the sample size for the trial using a grid search over potentially feasible sample sizes. The outcome measure was the difference in PEG at 24 weeks relative to baseline. The performance metric of interest in the simulation studies was how close the value of the estimated dynamic treatment regime, $V(\widehat{\mathbf{d}_n})$, was to the value of the optimal dynamic treatment regime $V(\mathbf{d}^{\text{opt}})$ for the difference. The percentage of optimal value is equal to $V(\widehat{\mathbf{d}_n})/V(\mathbf{d}^{\text{opt}})$ (assuming $V(\widehat{\mathbf{d}_n})$ is non-negative and $V(\mathbf{d}^{\text{opt}})$ is strictly positive). Note that this is not a hypothesis test but a performance criterion that evaluates how close the estimated treatment regime is to the optimal treatment regime

The estimated value of the estimated dynamic treatment regime for each replicate was obtained using Monte-Carlo methods and an independent out-of-sample data set. First, an out-of-sample data set was

generated using the same data generating distribution as the one used to generate the trial data for a given simulation scenario. A dynamic treatment regime is estimated on the replicate study data using Q-learning. Then for every dynamic treatment regime, the estimated DTR is used to assign the out-of-sample participants to treatment sequences, and the estimated value of the DTR calculated (the expected outcome under each treatment is known for all out-of-sample participants). Finally, the ratio of the value from estimated DTR to the optimal DTR is calculated.

The analog to power in this setting is the probability that the ratio of the value from a DTR estimated on a trial with sample size n relative to the value of the optimal DTR is greater than or equal to a fixed performance cutoff δ .

$$P(V(\widehat{d_n}) \div V(d^{\text{opt}}) \ge \delta)$$

We chose a performance cut-off δ of 0.9, so that for a simulated trial to be considered a success the value of the DTR estimated on that simulation replicate's data must be within 90% of the optimal DTR's value.

There is no analog to Type-I error for this because a null scenario would imply that all treatments are equally ineffective and no biomarkers matter, and in this situation any dynamic treatment regime is trivially optimal.

Simulations were conducted using R version 4.0.4

Simulation Data Generation

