The outcome after each stage, Y_t the outcome is defined as the difference in PEG between the follow-up visit at the end of the stage and the baseline PEG. The simulation outcomes are on the standardized effect size scale instead of the 0-10 scale. The outcome of interest, Y, is the difference in PEG at 24 weeks relative to baseline $Y = Y_2$.

Let $A_{t,k}$ denote the indicator function ${\bf 1}$ (Intervention k given for stage t) that is one whenever intervention k is given for stage t and zero otherwise. For the outcome after each stage, Y_t , denote the conditional expectation of Y_t given the history and intervention by $Q_t(H_t,A_t)=E[Y_t|H_t,A_t]$. Then the data generating model for one of the simulation scenarios with a single covariate associated with the outcome is:

$$\begin{split} Q_1(H_1,A_1) &= .1A_{1,0} + .25A_{1,1} + .3A_{1,2} + .4A_{1,3} + .3X_1A_{1,3} + .25X_2 - .25X_3 \\ Q_2(H_2,A_2) &= .1A_{2,0} + .25A_{2,1} + .3A_{2,2} + .4A_{2,3} + .3X_1A_{2,3} - .1A_{2,1}A_{2,2} - 1A_{2,1}A_{2,3} \\ &- .1A_{2,2}A_{2,3} + .25X_2 - .25X_3 \\ Y_1 &= Q_1(H_1,A_1) + \epsilon_1, \quad \epsilon_1 \sim N(0,1) \\ Y_2 &= Q_2(H_2,A_2) + \epsilon_2, \quad \epsilon_2 \sim N(0,1) \\ Y &= Y_2 \end{split}$$

Recall that in the first stage exactly one intervention can be given, while in the second stage one or two interventions may be given.

The covariates were generated independently with $X_1 \sim \text{Bern}(.5)$, $X_l \sim \text{Bern}(p_l)$, l=2,...,5 where and p_l ranges from 0.5 to 0.9 and X_l are coded to take values $\{-1,1\}$ instead of $\{0,1\}$ and an additional five normally distributed covariates N(0,.5). There were a total of ten covariates, one of which was

associated with the outcome through a treatment interaction, and two prognostic covariates that influence the outcome but was not associated with response to treatment. The $\,Q$ -functions were estimated using mis-specified models that included interaction terms for every treatment by covariate pair, and the models were fit by the Lasso.

These settings give rise to the following optimal rule:

X_1	A_1^{opt}	$A_2^{ m opt}$	Response to treatment at 24 weeks compared to baseline
$X_1 = -1$	Any intervention	$A_{2,1}$ and $A_{2,2}$ in combination	0.45
$X_1 = 1$	Any intervention	$A_{2,2}$ and $A_{2,3}$ in combination	0.9

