The optimal rule above, \mathbf{d}^{opt} , has an average (over the values of X_1) response of (0.45+0.9) = 0.675. An example DTR with a value that is within 90% of the optimal value is:

X_1	$A_1^{ m opt}$	$A_2^{ m opt}$	Response to treatment at 24 weeks compared to baseline
$X_1 = -1$	Any intervention	$A_{2,1}$ and $A_{2,2}$ in combination	0.45
$X_1 = 1$	Any intervention	$A_{2,1}$ and $A_{2,3}$ in combination	0.85

Which assigns $A_{2,1}$ instead of $A_{2,2}$ as part of the combination for biomarker positive patients in stage two. The average response (over the values of biomarker X_1) is 0.65.

The table below shows \mathbf{d}^{opt} and other treatment rules for comparison.

Treatment Regime	Average response to treatment at 24 weeks compared to baseline
d ^{opt} (incorporates phenotypic markers)	0.675
Assign A_0 in both stages	0.1
Assign A_1 in both stages	0.25
Assign A_2 in both stages	0.3
Assign A_3 in both stages	0.4
Assign A_3 in the first stage and $A_{2,2}$ and $A_{2,3}$ in combination in the second stage (no phenotypic markers)	0.6

The probability of attaining a value within at least 90% of the optimal value for this scenario is 81% based on 5,000 replicates (Monte Carlo standard error ≈ 0.009)

The treatment effect sizes were based on systematic review by the Agency for Healthcare Research and Quality^{18,59} and an internal review conducted by the experts on BACPAC's Interventions Working Group. The standardized treatment effect sizes were assumed to be 0.25 for ACT, 0.3 for Duloxetine, and 0.4 for EEMT. The effect size for enhanced standard of care was assumed to be 0.1. Subgroup-specific effects were constrained so that the population average treatment effect was equal to the effect sizes from the systematic review.

Simulation Results

A total of 630 complete cases yields 80% probability to attain a value within at least 90% of the optimal value. Assuming $^{\sim}15\%$ of participants fail to complete the study through the primary efficacy endpoint, a total sample size of approximately 740 randomized would be sufficient to achieve at least 90% of the possible reduction in PEG 80% of the time. The 15% drop-out is intended as an upper-bound, not the actual anticipated drop-out, and is based on a threshold provided by experts in this area where they would have serious concerns about any study having above this rate of drop-out.

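### The 81% that protocol 13.2 attaches to its printed scenario cannot be reproduced from the printed model and Lasso: at n=630 they give about 22–35% by default and at most about 65–71% under favourable penalty choices

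*Protocol*

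**What the plan says.** Section 13.2 replaces power with the probability that the estimated regime attains a set fraction of the optimal regime's value: "We chose a performance cut-off δ of 0.9". It describes this as a performance criterion, not a test ("There is no analog to Type-I error for this").

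The section then prints one scenario: Stage 1 and Stage 2 outcome equations with error SD 1, ten covariates, and effect sizes ("The standardized treatment effect sizes were assumed to be 0.25 for ACT, 0.3 for Duloxetine, and 0.4 for EEMT", with 0.1 for enhanced self-care). The fitted models "included interaction terms for every treatment by covariate pair, and the models were fit by the Lasso". A table gives the optimal regime a value of 0.675 and the best listed regime without phenotypic markers 0.6.

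For that scenario it reports: "The probability of attaining a value within at least 90% of the optimal value for this scenario is 81% based on 5,000 replicates". Under the results it states: "A total of 630 complete cases yields 80% probability to attain a value within at least 90% of the optimal value". Section 4.1 repeats this ("the sample size of 630 will result in having approximately 80% probability of estimating a DTR within 90% of the optimal DTR"), and section 7.1 expresses it per randomised participant ("the sample size of 740 randomized will result in having approximately 80% probability of estimating a DTR within 90% of the optimal DTR"). The SAP's sample size paragraph only refers back to the protocol.

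**The concern.** The printed scenario looks too hard for an 81% success rate. Competing Stage 2 options differ by only 0.05–0.15 SD within a stratum of X1. The rule that ignores X1 falls just short of the bar, so success requires finding the one real interaction among 40 candidates while the penalty also shrinks the treatment effects.

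This probability is the sole justification of the sample size. If the printed scenario does not yield it, either the scenario is misdescribed or the figure is wrong. In both cases a reader cannot tell how likely the trial was to recover a near-optimal regime, which matters when the estimated regime is interpreted.

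**Working it through.** **1. Inputs, all from 13.2.** Stage 2 main effects are 0.10 (A0), 0.25 (A1), 0.30 (A2) and 0.40 (A3). The X1×A3 term is 0.30, each pair among A1–A3 carries −0.10, the prognostic terms are .25X2 − .25X3, and the error SD is 1. The A1×A3 coefficient is printed as −1, but the section's own 0.85 requires −0.10: 0.25 + 0.40 + 0.30 − 0.10 = 0.85. I use −0.10.

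**2. The printed value scale reproduces.**
- X1 = −1, A1 with A2: 0.25 + 0.30 − 0.10 = 0.45.
- X1 = 1, A2 with A3: 0.30 + 0.40 + 0.30 − 0.10 = 0.90.
- Optimum: (0.45 + 0.90)/2 = 0.675 (the protocol omits the division by 2; its result is right).
- Bar: 0.9 × 0.675 = 0.6075.
- A2 with A3 for everyone: (0.30 + 0.90)/2 = 0.60, and 0.60/0.675 = 0.889, a fail.

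**3. The success probability.** Data were simulated from the printed Stage 2 model. A Lasso with 54 terms (4 treatments, 10 covariates, 40 interactions) was fitted, the best of the ten Stage 2 options (4 single, 6 paired) was chosen for each covariate profile, and the rule's true value was compared with 0.6075. Runs used 200 to 1,500 replicates, so the Monte Carlo error is about 1–3 points.

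| Estimator | n=630 | n=740 |
|---|---|---|
| Lasso, all terms penalised, cross-validated penalty | 22–35% | 31–39% |
| Same, more conservative one-standard-error penalty | 13–21% | – |
| Treatment and covariate main effects unpenalised | 45–47% | – |
| Only treatment main effects unpenalised | 58–66% | 66–67% |
| Only treatment main effects unpenalised, penalty tuned on the truth | 65–71% | about 71% |
| Least squares told the true terms in advance | 74–80% | – |

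The ranges cover different p_l patterns, standardised or unstandardised covariates, treatment-pair terms in or out, and Stage 2 assignment either uniform or driven by response. For the latter, response-group shares of 20/20/40/20 were assumed because the protocol gives none. Taking the −1 literally gives 21% with the default Lasso.

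As a measure of the gap, the default Lasso reaches 66% at n=1,260 and 86% at n=2,000. With treatment main effects unpenalised it reaches 75% at n=1,000 and 84% at n=1,260.

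**4. A route that does reach about 82%.** Leave treatment main effects unpenalised, count the prognostic terms in the value, and take p2 = 0.9 and p3 = 0.5, which lie inside the printed range. With −1/1 coding the mean of X2 is 2 × 0.9 − 1 = 0.8, which adds 0.25 × 0.8 = 0.20 to every regime. The optimum becomes 0.675 + 0.20 = 0.875 and the no-phenotype rule 0.60 + 0.20 = 0.80. Then 0.80/0.875 = 0.914, which passes with no phenotype used. This contradicts the printed 0.675 and 0.6.

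**5. Adjacent checks.** √(0.81 × 0.19/5,000) = 0.0055, not the printed 0.009, which would correspond to 0.1539/0.009² ≈ 1,900 replicates. The step from 630 to about 740 is sound: 630/0.85 = 741. The standard error discrepancy is under half a point and does not explain the gap, but it suggests that the text was not reconciled with the code.

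**The case against.** The strongest reply is that 13.2 does not print enough for anyone to reproduce the figure, so failing to do so proves little. It omits the individual p_l, the tuning rule, which terms are penalised, the Stage 2 assignment shares, whether the prognostic terms count in the value, and the n behind the 81%. These choices move the answer by tens of points, as the table shows. This stands, and it is why the point concerns reproducibility and not a proven arithmetic error. It does not rescue the 81%: on the printed 0.675 scale no Lasso variant tried reached it at n=630.

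The headline 80% also has some independence. Section 13.2 presents the equations as one of several scenarios and describes a grid search over sample sizes, and the SAP cites a separate statistical design paper that is not available here. That stands too. The 81%, however, is tied explicitly to the printed scenario.

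A reader might infer that about 80% is attainable only by an analyst who already knows the tailoring marker. The documents do not support that, because step 4 reaches it without such knowledge, at the price of contradicting the printed values.

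Finally, section 13.4.1 fixes Q-learning but leaves the regression procedure open. The SAP reports 805 randomised and 683 randomised to Stage 2, and a planning probability does not bias the estimated regime. All of this is correct, and it limits the point to the stated justification.

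**Conclusion.** The 81% does not follow from the printed scenario on its printed scale. The shortfall at n=630 is roughly 46–59 points for a default Lasso (81 − 35 to 81 − 22) and roughly 10–16 points for the most favourable variant tried, whose penalty was tuned on a truth that no analyst would have (81 − 71 to 81 − 65). Either the scenario is misdescribed or the figure needs correcting.

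This rests on reading the A1×A3 coefficient as −0.10, on p_l values within 0.5–0.9, on assumed Stage 2 assignment shares, and on letting any Stage 2 option follow any first-stage treatment, as the printed optimal rule does.

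A reader might go further and conclude that the trial's real success probability is about 25%, or that the 80% is shown to be false. The documents do not support either. The penalty settings behind the simulation are unknown, the 80% may draw on unprinted scenarios, and the Lasso is not fixed as the primary estimator.

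**What to change.** 1. Re-run the archived code for this scenario at n=630.
2. Print in 13.2 the n, the individual p_l, the tuning rule, the penalised terms, the Stage 2 assignment shares and whether the prognostic terms enter the value. Correct the A1×A3 coefficient and the Monte Carlo standard error at the same time.
3. Correct whichever is wrong, the scenario description or the 81%. If the prognostic terms are counted, restate the 0.675 and 0.6 and say openly whether the no-phenotype rule meets the criterion.
4. If the re-run does not support the 80%, restate it in 4.1, 7.1 and 13.2 as the reproduced figure or as a range over penalty choices. If it rests on other scenarios, name and summarise them.

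No replacement value should be written in before the re-run, and this point asks for no change to the primary analysis. The cost is a simulation re-run and some text, with possibly a less favourable stated figure, and no extra patients.

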13.3. POPULATIONS FOR ANALYSES

All participants

The "All participants" population will consist of all participants consented to the study.

All Randomized Population

The All Randomized population will consist of all participants randomized and statistical analyses will follow the intention to treat approach as much as possible. The All Randomized population will be used in primary, secondary, and exploratory analyses.

13.4. STATISTICAL ANALYSES

13.4.1.GENERAL APPROACH

Below we provide an overview of the general statistical approach planned for this trial. A complete and detailed statistical analysis plan (SAP) will be completed prior to any evaluation of primary or secondary outcome data stratified by treatment group or sequence.

The primary goal will be to estimate a two-stage dynamic treatment regime that maximizes the expected reduction in PEG between the beginning and the end of the study. We will use Q-learning for this approach. ⁵ Q-learning reduces the reinforcement learning problem of optimizing a two-stage dynamic treatment regime to a standard regression problem, after which standard regression algorithms can be applied. A secondary interest will be to estimate a two-stage DTR that minimizes some combination of multiple outcomes, where the ideal trade-off is estimated using participant preferences. Here we will use a latent variable approach: We will assume that that the optimal combination, or preferred trade-off, of outcomes for each individual can be represented as a simple convex combination of outcomes, where the participant-specific weights of the convex combination are unobserved and depend on the participant's covariates and responses to questionnaires. To estimate and make inferences on these weights, we will estimate the posterior distribution of these latent weights conditional on the covariates and questionnaire responses. This is what was proposed, for example, in Butler 2016.⁶⁷ Other objectives include assessing long-term effectiveness of embedded and estimated treatment regimes and conducting hypothesis tests to compare the effectiveness of individual treatments and nested treatment regimes. Comparisons of first-stage treatments and of second-stage treatments adjusted for first-stage treatments can be conducted using standard t-tests. Comparisons of nested DTRs can be conducted using the methodology discussed in Kosorok and Moodie 2016.⁶⁸ Estimation and assessment of DTRs based on longer-term outcomes can be conducted using Q-learning. The methods used for conducting inference and variable importance analysis of the Q-functions will depend on the data at hand and the regression procedures chosen. However, one possible contender is the bootstrapping method of Chakraborty, Laber and Zhao 2013.⁶⁹

We expect missing data to be minimal because of study procedures discussed previously to enhance retention such as incentives, incorporation of patient stakeholder feedback in the development of study materials, and efforts to minimize participant burden. In addition, there will be ongoing participant engagement through a study website, contact with research staff and regular patient engagement efforts. Finally, protocols for discontinuation of study treatment that are not tolerated are planned to enhance retention. We will continue to follow all participants until the end of the study and will utilize alternative forms of data collection for those who do not attend planned study visits (e.g., telephone administration or online data collection). Despite these efforts, missing data will arise and, as needed and appropriate, will be addressed using non-parametric multiple imputation procedures. Sensitivity analyses will be presented in detail as part of the SAP.

13.4.2.ANALYSIS OF THE PRIMARY EFFICACY ENDPOINT(S)

Complete details will be provided in the formal Statistical Analysis Plan for the study.

13.4.3.ANALYSIS OF THE SECONDARY ENDPOINT(S)

Complete details will be provided in the formal Statistical Analysis Plan for the study.

13.4.4.SAFETY ANALYSES

No safety analyses are planned other than descriptive summaries and data listings of reported adverse events.

13.4.5.BASELINE DESCRIPTIVE STATISTICS

Complete details will be provided in the formal Statistical Analysis Plan for the study.

13.4.6.PLANNED INTERIM ANALYSES

No interim analyses are planned for the study. Adaptation to the design, *i.e.* the second stage randomization probabilities, is planned and details will be included in a future Statistical Analysis Plan. Briefly, overall proportions of participants assigned to augment or switch will be monitored. If proportions deviate meaningfully from assumptions, we will consider shifting randomization probabilities within Group 3 (*e.g.*, from 50/50 to 60/40 augment/switch).

13.4.7.SUB-GROUP ANALYSES

N/A

